### 12.2. Analysis Populations

*Safety/Intent-to-treat (ITT) Population* — all patients who received at least 1 dose of study treatment.

*Efficacy Evaluable (EE) Population* — all patients who completed  $\geq 1$  cycle of therapy or those who discontinued due to progressive disease or DLT.

*Per-Protocol (PP) Population* — all patients who have adequate data at baseline and at 1 or more scheduled post-treatment tumor assessment and have no major protocol deviations. For patients who discontinue study treatment for any reason and start another treatment of their malignancy, no subsequent response assessments will be used for efficacy evaluation.

### 12.3. Analysis of Safety

Safety analyses will be conducted on the Safety/ITT Population. Safety observations will be analyzed using descriptive statistics and tabulation. No formal statistical comparisons are planned. All safety data will be presented in listings.

- Safety Endpoints
  - AEs.
  - Concomitant medications.
  - Clinical observations (e.g., vital signs, physical examination).
  - Laboratory tests, (e.g., clinical chemistry, hematology, coagulation, urinalysis).
  - ECGs.
  - Injection site reactions.

- Analyses
  - TEAEs: by dose level, intensity, and relationship to investigational product.
  - Treatment-emergent changes in severity grade of laboratory tests (see [Section 10.4.5](#)) will be summarized as “shift tables.”
  - Descriptive statistics will be summarized for vital signs and ECG parameters by dose level and visit.
  - Concomitant medications will be summarized by WHO Drug Class and ATC text.
  - Injection site reactions will be summarized by incidence for each dose group and overall by worst grade on study. Time-to-event analyses will be performed for injection site reactions.

## 12.4. Analysis of Treatment Effect

Analyses of treatment effect will be performed on both the EE and PP populations.

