## 6.3. Dose-escalation Procedures

### 6.3.1. ***Definition of a Dose-Limiting Toxicity and Dose Modifying Event***

The safety and tolerability of IMO-8400 will be assessed using reported and observed AEs as well as scheduled safety observations including vital signs, physical examination, laboratory tests (hematology, chemistry, and coagulation), urinalysis, and electrocardiograms (ECGs).

A DLT can be either a clinical or laboratory AE.

A potential DLT event is defined as a treatment-emergent AE (see [Section 10.1](#)) which occurs within the first 5 weeks of treatment and meets *any* of the following criteria using NCI CTCAE grading (see [Section 10.4.4](#)):

- Is a clinical event of Grade 3 or higher severity, except for the following:
  - Alopecia
  - Grade 3 fatigue
  - Grade 3 nausea/vomiting that has not been treated with optimal anti-emetic treatments
  - Grade 3 diarrhea that has not been treated with optimal anti-diarrheal treatments
  - AE related to the underlying disease
- Is a confirmed laboratory finding of Grade 3 or higher severity (see [Section 10.4.5](#)) and has been assessed as related to IMO-8400 (any relationship other than “not related”) with the exceptions of neutropenia and thrombocytopenia. DLTs with respect to neutropenia/thrombocytopenia are outlined below:
  - Grade 4 neutropenia lasting > 7 days
  - Grade 3 or 4 neutropenia with a sustained temperature > 101.3° F
  - Grade 3 thrombocytopenia associated with clinically significant bleeding that requires transfusion therapy
  - Grade 4 thrombocytopenia

Clinically significant toxicities or TEAEs that meet the definition of dose-limiting but occurring after Week 5 of Cycle 1 are defined as dose modifying events (DMEs) and may be considered when determining the RP2D.

The Data Review Committee (DRC) is comprised of the Idera Medical Monitor and Investigators from participating sites. The DRC will review all potential DLT events to assess causality, i.e., relationship to study drug (see [Section 10.4.3](#)). Events will be considered DLT events unless they are unanimously assessed as “Not related,” that is, a factor other than study drug is the cause of the event (see [Section 10.4.3](#)).

The definition of a DLT event will be applicable in the following contexts:

- DRC review determining dose escalation (see below).
- DRC review in defining the MTD (see below) or RP2D.

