### 12.1. Sample Size Determination and Study Power

Following identification of the MTD/RP2D, up to an additional 22 patients will be enrolled at the MTD or proposed RP2D level. With a total sample size of 22 patients, there is a 90% probability to detect an AE with a true incidence rate of 10%. A secondary objective of this study is to determine the treatment effect of IMO-8400 in patients enrolled at the MTD/RP2D. Using the exact binomial distribution with a 1-sided test and an alpha of 0.05, there is 79% power to detect a response rate of 33% as compared to a null response rate of 10%.

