#### 12.4.1.2. Secondary Treatment Effect Parameters

The VIth International Workshop specifies a number of outcome metrics related to time [1] (see [Section 16.3](#)). The following parameters are considered most relevant to this time-limited study and will be analyzed both globally across all cohorts and by dose level.

- Distribution of response categories by treatment group and overall.
- Time to progression – Time from the initiation of treatment to disease progression with deaths due to unrelated causes censored.
- Progression-free survival – Time from the initiation of treatment to disease progression or death from any cause.
- Time to best observed response – Time from the initiation of treatment to best observed category of response.

- Percent and absolute change in quantitative serum levels of monoclonal and total IgM.

Kaplan-Meier analyses will be used to analyze time to event data. Analysis of IgM data will be performed using a repeated measures mixed model. MyD88 L265P mutation status will be used as a covariate in statistical analyses.

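### Efficacy is analysed only in the EE and PP sets, so no planned response rate or time-to-event result counts every treated patient

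*Protocol*

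**What the plan says.** Protocol section 12.2 defines three sets.

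- **Safety/ITT:** everyone who received at least one dose.
- **Efficacy Evaluable (EE):** patients who completed at least one cycle, "or those who discontinued due to progressive disease or DLT".
- **Per-Protocol (PP):** patients with adequate data at baseline and "at 1 or more scheduled post-treatment tumor assessment and have no major protocol deviations".

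Section 12.3 gives the first set its use: "Safety analyses will be conducted on the Safety/ITT Population". Section 12.4 then fixes the efficacy sets: "Analyses of treatment effect will be performed on both the EE and PP populations". Section 12.4.1.1 makes objective response rate (CR, VGPR, PR or MR) the primary treatment effect parameter. Section 12.4.1.2 adds time to progression, PFS and other measures, which "will be analyzed both globally across all cohorts and by dose level".

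Section 12.1 refers the efficacy objective to patients enrolled at the MTD/RP2D. For 22 patients and a 1-sided exact binomial test at 0.05 it says "there is 79% power to detect a response rate of 33% as compared to a null response rate of 10"%. It makes no allowance for patients who turn out not to be evaluable.

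**The concern.** A cycle lasts 8 weeks (section 1.4). A treated patient who stops during Cycle 1 stays in EE only if the reason is progression or DLT. Those lost are patients who stop for an adverse event that is not a DLT, who withdraw consent, who are lost to follow-up, or who die of a cause that is neither progression nor DLT. Under section 6.3.1, toxicity of DLT type that occurs after Week 5 of Cycle 1 is a dose modifying event and not a DLT. So a patient who stops for such toxicity in Week 3 is counted, and one who stops for the same toxicity in Week 7 is not.

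PP is selective in another way. It is not nested in EE and may keep some patients whom EE drops, for example those who leave after the Week 5 laboratory tests. It loses patients with no scheduled post-treatment assessment or with a major deviation. Neither set is certain to contain every treated patient.

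Patients who leave this early will mostly have no documented response. Removing them shrinks the denominator and leaves the numerator almost unchanged. The rate rises, and the number of responders needed for significance can fall. PFS is affected too: section 12.4.1.2 counts death from any cause, but on EE the Cycle 1 deaths that are neither progression nor DLT disappear.

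**Working it through.** **Inputs.** From section 12.1: n = 22, null rate 0.10, alternative 0.33, 1-sided exact binomial test at 0.05, stated power 79%. The protocol gives no exclusion rate, so q (the probability that a treated patient is outside EE) is an assumption and is varied.

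**The plan's own figure.** With X ~ Bin(22, 0.10), P(X ≥ 5) = 0.0621 and P(X ≥ 6) = 0.0182, so 6 responders are needed and the actual error is 1.8%. Power is P(X ≥ 6 | 22, 0.33) = 0.784, or 0.794 if 33% is read as one third. The stated 79% is reproduced.

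**Bias in the rate.** If nobody excluded responded, the EE rate is the all-treated rate divided by (1 − q). At q = 0.20 this gives 0.10/0.80 = 0.125 and 0.33/0.80 = 0.4125.

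**A fixed number dropped.** The exact cut-off depends on how many patients remain.

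| EE n | Responders needed | p-value with 4 | with 5 | with 6 |
|---|---|---|---|---|
| 22 | 6 | 0.172 | 0.062 | 0.018 |
| 21 | 6 | 0.152 | 0.052 | 0.014 |
| 20 | 5 | 0.133 | 0.043 | 0.011 |
| 17 | 5 | 0.083 | 0.022 | 0.005 |

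Dropping one non-responder changes no decision. Dropping two lowers the cut-off to 5, and the chance of success at an all-treated rate of 10% becomes P(X ≥ 5 | 22, 0.10) = 0.0621. Between n = 17 and n = 22, five responders is the only count whose result depends on the denominator.

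**A random number dropped.** Let m ~ Bin(22, 1 − q) be the size of EE and c(m) its exact 5% cut-off. With an all-treated rate of 10% and no responders among those excluded, the error is the sum over m of P(m) × P(X ≥ c(m) | m, 0.10/(1 − q)).

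| q | Error, EE not refilled | Error, EE refilled to 22: P(X ≥ 6 given 22, 0.10/(1 − q)) |
|---|---|---|
| 5% | 2.9% | 2.3% |
| 10% | 4.4% | 2.9% |
| 12.8% | 5.0% | 3.4% |
| 15% | 5.4% | 3.7% |
| 20% | 6.2% | 4.8% |
| 30% | 8.6% | 8.3% |

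This table averages over how many patients leave; the fixed-count result is conditional on exactly two leaving. That is why 10% exclusion averages 4.4% while two of 22 (9%) gives 6.2%.

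**If some of those excluded respond.** At a 5% response rate among them, the EE rate is (0.10 − 0.05q)/(1 − q). The error is 4.2% at q = 20% and 5.0% at q = 30%.

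**The case against.** The exact test appears only in the sample size section. Section 12.4 names no test of response against 10% and no decision rule. Response is a secondary objective, and section 6.10.1 describes the expansion as preliminary signal-seeking. If the 10% null describes evaluable patients rather than all treated patients, the EE test keeps its level (at most 0.044 for n from 14 to 22).

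The group lost is also narrower than it first looks. EE keeps those who stop for progression or DLT. Under section 6.3.1, a clinical event of Grade 3 or higher in the first 5 weeks is a DLT unless it falls under a listed exception, which includes events related to the disease, or is unanimously judged unrelated. A dose modifying event may lead to interruption and resumption, so it need not remove the patient. Because laboratory assessments fall at Week 5, EOT and EOS, PP may recover many Cycle 1 leavers. The figures above are for EE; PP has not been quantified.

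These points limit the size of the problem, and the type I error figures must be read as conditional. They do not remove the selective denominator. Section 12.1 speaks of patients enrolled at the MTD/RP2D, which favours the all-treated reading of the null. Replacement under section 6.6 is optional and tied to evaluability for dose review over the first 4 weeks, so it does not restore EE to 22. Nor is this a detail left to the SAP, because section 12.4 already names the efficacy sets.

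**Conclusion.** The concern holds and should be fixed. As written, no planned efficacy analysis has all treated patients as its denominator, although the protocol defines that set. The response rate is overstated whenever those excluded respond less often than those kept; at 20% exclusion of non-responders the inflation is a factor of 1.25. The effect on the test is modest and depends on the assumptions: the error stays below 5% up to about 13% exclusion and reaches 6.2% at 20% and 8.6% at 30%, if the true all-treated rate is 10%, nobody excluded responded and EE is not refilled. A Week 5 minor response followed by early exit is possible; it would also be lost from EE and would reduce the bias. If leaving is unrelated to response, the EE test keeps its level. The primary safety objective is unaffected.

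**What to change.** In section 12.4, name the Safety/ITT set as the main population for objective response rate. Base the exact test and confidence interval on all patients treated in the MTD/RP2D expansion, and count those without a documented response as non-responders. Analyse time to progression and PFS in the same all-treated set, globally and by dose level, with the usual censoring. Keep EE and PP as supportive analyses.

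This takes one or two sentences, carried into the SAP, and needs no new patients, visits or data. The reported rate may be slightly lower. There is also a cost in power if 33% is the rate only among patients who stay: P(X ≥ 6 | 22 − d, 0.33) is 74.1%, 69.2%, 63.7% and 57.6% for d = 1, 2, 3 and 4 early leavers, against 78.4% with none. If 33% is meant as the all-treated rate, power stays at 78.4%. Section 12.1 should say which is intended.

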### 12.4.1. *Assessments*

Laboratory assessments for disease status (see [Section 9.4.2](#)) will be conducted at Screening, every 4 weeks  $\pm$  1 week (Week 1 and Week 5 of each cycle), every 12 weeks  $\pm$  4 weeks during the Follow-up Phase, at the EOT visit, and at the EOS visit. Clinical assessments for disease status (see [Section 9.4.1](#)) will be conducted at Screening, every 8 weeks  $\pm$  1 week (Week 1 of every cycle), every 12 weeks  $\pm$  4 weeks during the Follow-up Phase, at the EOT visit, and at the EOS visit. Radiologic imaging will be performed at Screening and at EOT visit or as clinically indicated. Bone marrow biopsy and aspirate will be performed at Screening, EOT, and to document complete response as appropriate (see [Section 16.2](#)).

#### 12.4.1.1. Primary Treatment Effect Parameter

The primary treatment effect parameter is objective response rate, defined as the occurrence of CR, VGPR, PR, or MR.

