## 1. SYNOPSIS

### 1.1. Protocol Information

Protocol Number	8400-401
Protocol Title	Phase 1/2 Open-label, Multiple-dose, Dose-escalation Study to Evaluate the Safety and Tolerability of IMO-8400 in Patients with Relapsed or Refractory Waldenström's Macroglobulinemia
Sponsor	Idera Pharmaceuticals, Inc.
Name of Finished Product	IMO-8400 for Injection, 150 mg
Name of Active ingredient	IMO-8400
Phase of Development	1/2
Indication (Target)	Relapsed or Refractory Waldenström's Macroglobulinemia
Number of Patients	Approximately 60 patients in planned escalation and expansion cohorts; potential for additional patients in contingency cohorts or as replacements
Number of Sites	Multiple Centers in the US
Date first patient enrolled	Q2 2014
Est. date last patient enrolled	Q4 2016
Est. date last patient last visit	Q2 2017

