**Table-7. Clinical Studies with IMO-8400 in Addition to This Study**

Protocol No.	Protocol Title	Status
8400-001	A Phase 1, Single-Dose Escalation and 4-week Multiple-Dose Escalation Study of the Safety and Pharmacokinetics of IMO-8400 in Healthy Volunteers	Completed
8400-201	A Randomized, Double-Blind, Placebo-Controlled, 12-week Dose-Ranging Trial of IMO-8400 in Patients with Moderate to Severe Plaque Psoriasis	Completed
8400-402	Phase 1/2 Open-label, Multiple-dose, Dose-escalation Study to Evaluate the Safety and Tolerability of IMO-8400 in Patients with Relapsed or Refractory Diffuse Large B-cell Lymphoma and Presence of the MyD88 L265P Mutation	Ongoing
8400-404	An Extension Study to Evaluate the Long-Term Safety, Tolerability, and Clinical Activity of IMO-8400 in Patients with Relapsed or Refractory Waldenström's Macroglobulinemia who Completed Study 8400-401	Ongoing
8400-211	A Phase 2, Randomized, Double-Blind, Placebo-Controlled Trial of IMO-8400 in Patients with Dermatomyositis	Ongoing

Abbreviations: MyD88=Myeloid differentiation primary response gene (88)

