## 6.5. Management of Individual Patients

### 6.5.1. Duration of Treatment

Each enrolled patient will receive IMO-8400 at the assigned dose level until the earliest of:

- *Clinical DLT event* – see [Section 6.3](#).
  - Study treatment will be discontinued in patients determined to have a clinical DLT event until resolution and may only be resumed after discussion with an Idera Medical Monitor and agreement that it is in the patient's best interest to continue.
  - For a DME, provision is made for interrupting dosing for up to 3 weeks and, if the acute toxicity improves sufficiently, resuming treatment at a lower dose level based on discussion between the sponsor's designated medical monitor and the treating physician.
  - For DLT laboratory events, provision is made for pausing treatment for up to 3 weeks and, if the acute toxicity improves sufficiently, resuming treatment at a lower dose level (see [Section 6.5.2](#) for details).
  - The Investigator will review with the Medical Monitor decisions to discontinue, pause, and/or restart study treatment.
- *Disease progression* – based on scheduled assessments at Week 1 of each cycle. Unscheduled assessments may be conducted in response to new clinical observations. Disease status will be classified according to international guidelines [1] (see [Section 9.5](#) for details).
- *Termination of participation in the study* – due to AE, withdrawal of consent, intolerable toxicity, or loss to follow up.

In certain instances, patients may be deriving clinical benefit despite objective signs of progressive disease such as radiologic progression. It can be anticipated that based on the study drug's mechanism of action, through an immunologic mediated effect, signs of radiologic response may be delayed. Based on these considerations, continuing to treat some patients past progressive disease may be considered after discussion between the Sponsor and Investigator, provided the following conditions are met:

- Patient has not achieved an objective response on study and then developed progressive disease;

- Patient has not experienced a period of clinically significant stable disease on study and then developed progressive disease;
- Patient must be re-evaluated 4 to 6 weeks after initial progression in order to confirm progressive WM disease;
- If the follow-up assessment does not confirm progressive disease, patient may resume regularly scheduled follow-up per protocol;

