## **6.9. Criteria for Study Termination**

The study ends approximately 6 months following enrollment of the last patient. The Sponsor reserves the right to discontinue or suspend the study earlier for safety or administrative reasons at any time, at an individual site or overall. Should the study be terminated and/or the site closed for whatever reason, all study documentation must be archived and study medication must be destroyed according to local policy or returned to the Sponsor or its representative per Sponsor's instructions.

If the trial is terminated prematurely or suspended, the Sponsor will promptly inform the participating Investigators and institutions, the regulatory authorities, and the Institutional Review Board (IRB) of the termination or suspension and the reason(s) for the action.

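### Response by dose level has no time window, while possible observation time depends on enrolment order and hence on dose

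*Protocol*

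**What the plan says.** - **Endpoint.** Section 12.4.1.1 names as primary treatment effect parameter the "objective response rate, defined as the occurrence of CR, VGPR, PR, or MR". No time point or window is attached.
- **Use by dose.** Section 12.4.1.2 lists the distribution of response categories among measures chosen as relevant to this "time-limited study and will be analyzed both globally across all cohorts and by dose level". Section 6.4 gives the dose dependence of clinical response as the purpose of the expansion cohorts. Section 5.2 makes the choice of an optimal dose a secondary objective.
- **Duration.** Section 6.7 leaves maximum exposure undefined. Section 6.10.2.2 continues treatment until progression, intolerable toxicity, withdrawal of consent or study completion. It also follows patients who stop for reasons other than progression, up to a common cut-off.
- **Cut-off.** Section 6.9: "The study ends approximately 6 months following enrollment of the last patient".
- **Calendar.** Section 1.1: "Date first patient enrolled Q2 2014"; "Est. date last patient enrolled Q4 2016"; "Est. date last patient last visit Q2 2017".
- **Order of enrolment.** Under Section 6.3.3 a higher dose level opens after review of the one before. Under Section 6.4 the RP2D expansion follows once an MTD or potential RP2D is established.
- **Extension study.** Table-7 lists 8400-404, for patients with "Waldenström's Macroglobulinemia who Completed Study 8400-401".

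**The concern.** A proportion of patients who ever responded can only rise as observation lengthens. Here the time available is set by enrolment date, and enrolment date is linked to dose level. Two equally active doses can then show different response rates because their patients were watched for different periods. Kaplan-Meier methods deal with unequal follow-up for time to progression and progression-free survival, but they do nothing for a crude response proportion or a table of response categories.

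At stake is the reading of dose dependence and the choice of an optimal dose. The protocol itself suggests that timing may differ by dose: Section 6.10.2.1 reports a faster time to response at the highest dose level then studied. If so, the length of the window affects the comparison.

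**Working it through.** **1. The plan's own figures (Section 12.1).** With n = 22 and an exact one-sided binomial test at 0.05:

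- P(X ≥ 5 | 10%) = 0.0621, which exceeds 0.05.
- P(X ≥ 6 | 10%) = 0.0182, so at least 6 responders are needed.
- Power = P(X ≥ 6 | 33%) = 0.784, or 0.794 if the alternative is read as 1/3. The stated 79% is reproduced.
- Adverse event detection: 1 − 0.9^22 = 0.9015, which reproduces the stated 90%.

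**2. Possible observation time (Sections 1.1 and 6.9).**

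- Earliest patients, Q2 2014 to Q2 2017: 30 June 2014 to 1 April 2017 is 33 months; 1 April 2014 to 30 June 2017 is 39 months.
- Last patients: about 6 months by Section 6.9. The synopsis quarters alone would allow 3 to 9 months.
- Ratio of ceiling to minimum: 33/6 = 5.5 to 39/6 = 6.5.
- Four-weekly IgM assessments: 26/4 = 6.5, so about 6 in six months, against 156/4 = 39 in 36 months. This compares extremes: 39 requires a first-enrolled patient who never progresses, stops or transfers.

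**3. Why the ceiling is probably not reached.** The Revision History records that version 6.0 (13 August 2015) first allowed patients with clinical benefit to continue on this study. Section 4.4.1 says 19 patients had been treated by August 2015. Table-7 shows an extension study for those who completed this one. Some early patients therefore probably left well before 2017, which shortens observation at the early dose levels.

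**4. What late responses would do (assumptions, not protocol data).** If a fraction f of eventual responses falls after Month 6, a dose with a true 33% rate shows 0.33 × (1 − f) in patients watched for 6 months:

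- f = 0: 33.0%
- f = 0.10: 29.7%
- f = 0.30: 23.1%

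A second illustration uses a constant monthly hazard of first response h1 and a competing exit hazard h2 = ln 2 / (median time to exit). The rate seen by month T is F(T) = h1/(h1+h2) × [1 − exp(−(h1+h2)T)], with h1 chosen so that F(6) = 20%. For a 12-month exit median, h2 = 0.0578 and h1 is about 0.0446. The drug effect is identical in every column:

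| Assumed median time to exit | 6 months | 12 months | 24 months | 36 months |
|---|---|---|---|---|
| 6 months | 20.0% | 27.3% | 30.9% | 31.4% |
| 12 months | 20.0% | 30.8% | 39.8% | 42.5% |
| 24 months | 20.0% | 33.2% | 47.5% | 53.8% |

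A constant hazard builds in late responses. If all responses came by Month 6, every row would read 20% throughout.

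**5. The 10% and 33% rates have no horizon.** Under the same model, a 10% rate at 6 months becomes 14.3% at 12 months (exit median 6 months) to 19.0% (no exit). P(X ≥ 6 of 22) then moves from 0.018 to between 0.083 and 0.228. What the 10% benchmark means depends on the period to which it refers.

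**The case against.** The strongest reply is that Section 12 leaves data handling and further efficacy methods to the SAP, and a best-response window is often set there. That is fair as far as it goes. But the protocol states the endpoint itself, without a window, and states its use by dose level. Section 12.7 defers censoring rules, which do not repair a crude proportion.

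The other points limit the size of the problem, and they stand:

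- A reader might infer that the first cohort was actually watched for three years, or that lower doses are favoured. The documents support neither. Three years is a ceiling, and early departure or transfer to 8400-404 could shrink or reverse the gap.
- The protocol documents no responses after Month 6. The remark in Section 6.5.1 that "signs of radiologic response may be delayed" concerns imaging, which is scheduled only at Screening and end of treatment, whereas the lowest level counted as a response is defined by IgM change. Section 9.5 recommends at least 12 weeks before calling a patient unresponsive, about half of the shortest planned follow-up. An indolent disease course (Section 4.1) is not evidence of slow response.
- By-dose response is secondary, with 3 to 6 patients initially per escalation cohort and no formal between-dose test stated. The Kaplan-Meier analyses and the repeated-measures IgM model give readers other information, although they leave the response proportions uncorrected.
- A reader might also infer that the test against 10% is confounded in the same way. It is not, because it concerns a single dose level.

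**Conclusion.** The concern holds in a limited form. By-dose response proportions mix dose with observation time, because the endpoint has no window and possible follow-up depends on enrolment order. Potential observation ranges from about 6 months to a ceiling of 33 to 39 months, with realised times probably shorter.

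Neither the direction nor the size of the bias can be determined from the protocol. The percentages for late responses are illustrations that rest on assumed late-response fractions or hazards, and the bias is zero if all responses occur within about 6 months. The 79% power figure stands. The RP2D test is not confounded by dose, but its 10% and 33% should be tied to a stated period.

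**What to change.** In Sections 12.4.1.1 and 12.4.1.2, base by-dose comparisons of response rate and response category on best response within one common window of about 24 weeks, counted in calendar time from first dose. Use scheduled assessments, or the end-of-treatment assessment, that fall inside it. Report the same-window rate for the RP2D cohort.

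The window should not be tied to the start of Cycle 4. Without delay that visit is on Day 169, or Day 176 with the one-week allowance, against about 182 days (26 × 7) of guaranteed follow-up. Cycle weeks are counted from each cycle's own first injection, so a 3-week interruption moves the visit to about Day 169 + 21 = 190, possibly after study end. A limit such as Day 176 would take in an on-time Week 25 assessment and stay inside the 6 months.

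Keep best response at any time, reported with median observation time per dose level and with patients who moved to 8400-404 identified.

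The cost is one additional table and no new visits. Responses first seen after about 24 weeks will not count in the by-dose comparison, which would understate a dose that acts slowly; the any-time table would still show them.
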